11.2 Analysis of Adverse Events

The number and percentage of subjects having treatment-emergent adverse events will be tabulated by MedDRA system organ class and preferred term. The tabulations will also be provided with further breakdowns by NCI CTCAE toxicity grade and relationship to

study drug (ABT-414/TMZ/lomustine). Serious adverse events, adverse events leading to discontinuation of treatment, and adverse events leading to death will be summarized.

An overview of AEs will be presented, by treatment arm and overall, consisting of the number and percentage of subjects experiencing the following adverse event categories.

- Any treatment-emergent adverse event
- Any treatment-emergent adverse event by NCI CTCAE grade
- Any treatment-emergent adverse event with NCI CTCAE grade 3, 4 or 5
- Any treatment-emergent adverse event NCI CTCAE grade 3 or 4
- Any treatment-emergent adverse event that is rated as a reasonable possibility of being related to ABT-414
- Any treatment-emergent adverse event that is rated as a reasonable possibility of being related to TMZ
- Any treatment-emergent adverse event that is rated as a reasonable possibility of being related to lomustine
- Any treatment-emergent adverse event NCI toxicity grade 3 or 4 that is rated as a reasonable possibility of being related to ABT-414
- Any treatment-emergent adverse event NCI toxicity grade 3 or 4 that is rated as a reasonable possibility of being related to TMZ
- Any treatment-emergent adverse event NCI toxicity grade 3 or 4 that is rated as a reasonable possibility of being related to lomustine
- Any treatment-emergent serious adverse event
- Any treatment-emergent serious adverse event NCI toxicity grade 3 or 4
- Any treatment-emergent serious adverse event that is rated as a reasonable possibility of being related to ABT-414
- Any treatment-emergent serious adverse event that is rated as a reasonable possibility of being related to TMZ
- Any treatment-emergent serious adverse event that is rated as a reasonable possibility of being related to lomustine
- Any treatment-emergent adverse event leading to discontinuation of ABT-414

- Any treatment-emergent adverse event leading to discontinuation of TMZ
- Any treatment-emergent adverse event leading to discontinuation of lomustine
- Any treatment-emergent adverse event leading to dose reduction of ABT-414
- Any treatment-emergent adverse event leading to dose reduction of TMZ
- Any treatment-emergent adverse event leading to dose reduction of lomustine
- Any treatment-emergent adverse event leading to interruption of ABT-414
- Any treatment-emergent adverse event leading to interruption of TMZ
- Any treatment-emergent adverse event leading to interruption of lomustine
- Any treatment-emergent adverse event of special interest
- Any treatment-emergent adverse event leading to death

The treatment-emergent adverse events of special interest will be based on microcystic keratopathy CMQ 80000152 (Section 11.2.1).

Additionally, selected analyses of adverse events will be performed for the subset of subjects with EGFRvIII mutation (on an as-treated basis in the Ev3M population) for the following categories.

- Any treatment-emergent adverse event (descending frequency)
- Any treatment-emergent serious adverse event
- Any treatment-emergent adverse event of special interest

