In the ongoing phase I study, as of April 29 2015, 40 subjects have been treated in Arm B and 42 in Arm C. Common treatment emergent AEs in at least 30% of subjects in Arm B included photophobia (15/37.5%), blurred vision (23/57.5%), nausea (19/47.5%), fatigue (17/42.5%) and headache (12/30%); in Arm C, they were blurred vision (25/59.5%) and fatigue (24/57.1%). Grade 3/4 AEs found in > 10% of subjects in Arm B included keratitis (5/12.5%), gamma GT elevation (4/10%) and decreased platelet (4/10%); in Arm C, the only grade 3/4 AEs of > 10% was keratitis (6/14.3%). Overall, in the 1.25 mg/kg dose cohort the grade 3/4 ocular toxicity rate was 27%. ABT-414 administration was suspended in those who developed grade 3/4 eye toxicity until symptoms recovered to grade 1, which took a median of 40 days.

Because of the high rate of significant eye toxicity and the need for drug interruption, the starting dose of ABT-414 for the present study for both Arm 1 and 2 will be 1.00 mg/kg.

Additional Safety Information:

Preliminary safety data were available for 488 subjects who received at least 1 dose of ABT-414 in 4 open-label studies at the most recent IB update (version 7.0). This Phase 2 Study M14-483 (INTELLANCE-2) in recurrent GBM is the only trial for which safety data from a control arm (TMZ or lomustine monotherapy) is available. Adverse events reported for more than 20% of subjects receiving ABT-414

were fatigue (34.9%), vision blurred (27.3%), headache and keratitis (25.0% for each), dry eye (24.4%) and corneal epithelial microcysts (22.1%). The majority of subjects who received ABT-414 (77.3%) experienced at least 1 Treatment Emergent Adverse Event coded to the Standard Organ Class of Eye Disorders. In addition to ocular side effects related to corneal epitheliopathy, treatment-emergent adverse events reported by $\geq 10\%$ of subjects in the ABT-414 treatment groups and $\geq 5\%$ more frequently than the lomustine/TMZ control group included headache, fatigue, constipation, and liver transaminase elevations (alanine aminotransferase and aspartate aminotransferase). The rate of constipation was mainly accounted for by the ABT-414/TMZ combination arm, for which the rate was similar to that of subjects receiving TMZ monotherapy.

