5.4 Withdrawal criteria

Whatever the disease status, study treatment will be discontinued in case of:

- ◆ disease progression
- ◆ patient refusal
- ◆ intolerable toxicity precluding further protocol therapy
- ◆ patient's best interest
- ◆ start of any other anti-cancer agent/modality (surgery at recurrence is allowed)
- ◆ pregnancy

Patients discontinuing therapy in the absence of progression should not receive other cancer treatment before their disease progresses, unless this is clearly not in the interest of the patient. If, after treatment discontinuation, there is additional clinical information leading the investigator to conclude that the reason for discontinuation is no longer valid (except for toxicity), the subject may resume study treatment as long as no other chemotherapy, radiotherapy, immunotherapy, NovoTTF, or other treatment with antineoplastic intent has been received, with the exception of surgical intervention that yields histology not demonstrative of tumor progression. In case of toxicity in the combination arm that is

clearly attributable to either TMZ or ABT-414, that drug can be discontinued and the other can be continued. Patients that discontinue study treatment for toxicity, patient refusal and other reasons remain 'on study' and must be followed according to the follow-up schedule for progression, survival etc unless patient specifically withdraws consent from all further data collection for the study (this decision should be clearly documented e.g in the medical notes).

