4.4 Sample Size

This is a comparative randomized, open label, multicenter, multi-arm, Phase II study. Overall Survival (OS) is the primary endpoint.

Based on a one-sided logrank test, at an overall significance level of 2.5% and a power of 91.7% (accounting for the global testing strategy), a total of 118 deaths per comparison (i.e., monotherapy ABT-414 versus control and combination ABT-414 + TMZ versus control) are needed to detect a Hazard Ratio (HR) equal to 0.54 (i.e., a reduction in the hazard of death of 46%). A median OS of 7 months is expected on the control arm (Arm 3) based on literature review. The target treatment effect is assumed to be the same for both treatment arms (Arm 1 and Arm 2) and corresponds to an increase of median OS

to 12.9 months under proportional hazards. It is assumed that median PFS is 2.6 months on the control arm and 4.8 months on the treatment arms corresponding to an HR of 0.54.

The treatment effect on OS and PFS is generally expected to be positive correlated following historical trends.² Since the interim futility criterion (see Section 4.5 below) is primarily based on a PFS effect, the power of the study increases with the strength of association between PFS and OS. If PFS and OS effects are independent, the overall power of the study is estimated to be approximately 85%. The study is therefore expected to have at least 85% power overall as long as OS and PFS are not negatively correlated.

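### General adverse event tables are crude percentages over a window tied to treatment time; under the design PFS medians that window would be about 1.6 times longer on ABT-414

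*SAP*

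**What the plan says.** **Summary measure.** SAP 11.2: "The number and percentage of subjects having treatment-emergent adverse events will be tabulated by MedDRA system organ class and preferred term". The overview rows, including serious events and events of grade 3 or higher, are also numbers and percentages of subjects. Protocol 8.2.3.7 uses frequencies and percentages as well.

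**Counting window.** SAP 11.1 counts events that start or worsen after the first dose and no later than 35 days after the last dose. The rule is the same in all arms, but the window lengthens with treatment.

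**What ends treatment.** Protocol 5.4: "Whatever the disease status, study treatment will be discontinued in case of" any of several listed events, of which progression is the first; others include refusal and intolerable toxicity. Protocol 5.3 caps lomustine at one year.

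**Design effect.** SAP 4.4 assumes "median PFS is 2.6 months on the control arm and 4.8 months on the treatment arms corresponding to an HR of 0.54".

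**What else is planned.** SAP 9.2 summarises duration of exposure by arm, separately from the event tables. SAP 11.2.1.2 gives Kaplan-Meier time to onset, but only for events of special interest (microcystic keratopathy). SAP 11.1 rules out between-arm safety comparisons, p-values and confidence intervals. Neither document plans an incidence per patient-time or a fixed-horizon incidence for general treatment-emergent events.

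**The concern.** A crude percentage is comparable across arms only if subjects are observed for similar lengths of time. Here the observation window is treatment time plus 35 days, and treatment normally runs to progression. If ABT-414 delays progression as the design assumes, its patients are observed longer, and events unrelated to any study drug have more time to occur. Events expected from glioblastoma itself, such as the headache and seizure terms in Protocol Appendix H, are plausible candidates. The planned tables could not separate such accumulation from a drug effect.

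The distortion would run against ABT-414 and would be largest when the drug delays progression most. At stake is how the benefit-risk balance is read in a positive trial, not any hypothesis test.

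**Working it through.** **1. The plan's own figures.** SAP 4.4 gives "Based on a one-sided logrank test, at an overall significance level of 2.5% and a power of 91.7"%, with "a total of 118 deaths per comparison", which "are needed to detect a Hazard Ratio (HR) equal to 0.54". The Schoenfeld formula with 1:1 allocation within a comparison gives power = Φ(√118 / 2 × |ln 0.54| − 1.96) = Φ(3.347 − 1.960) = 0.917, so the figure reproduces. The PFS hazard ratio implied by the medians is 2.6/4.8 = 0.54, as stated.

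**2. Window length.** Assume that time on treatment is exponential with the design PFS median. The tail is 35/30.4375 = 1.15 months.
- Medians: control 2.6 + 1.15 = 3.75 months; ABT-414 4.8 + 1.15 = 5.95 months; ratio 1.59.
- Means: control 2.6/ln 2 + 1.15 = 4.90; ABT-414 4.8/ln 2 + 1.15 = 8.07; ratio 1.65.

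The ratio of PFS medians alone is 4.8/2.6 = 1.85. The shared tail pulls the window ratio down to about 1.6.

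**3. Effect on crude percentages.** Let r be the monthly hazard of a first event, equal in all arms, and λ = ln 2 / median PFS (0.267 control, 0.144 ABT-414). Then

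P(event) = 1 − exp(−1.15 r) × λ / (λ + r).

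The documents give no background event rates, so r is solved from an assumed control percentage. For a control percentage of 10%, r = 0.022:
- Control: 1 − 0.975 × 0.267/(0.267 + 0.022) = 10.0%.
- ABT-414: 1 − 0.975 × 0.144/(0.144 + 0.022) = 15.5%.

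| Control (assumed) | r per month | ABT-414, no drug effect | Difference, points |
|---|---|---|---|
| 5% | 0.011 | 8.0% | 3.0 |
| 10% | 0.022 | 15.5% | 5.5 |
| 20% | 0.049 | 29.2% | 9.2 |
| 35.2% | 0.10 | 47.3% | 12.2 |

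The difference peaks at 12.6 points, for a control percentage of about 44%.

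**4. Sensitivity**, for control percentages of 10% / 20%:
- True PFS hazard ratio 0.70: 2.9 / 5.0 points. At 0.91: 0.7 / 1.2. At 1.0: zero.
- Front-loaded event hazard (Weibull shape 0.5): 2.4 / 4.3.
- Treatment cut at 12 months in every arm: 4.1 / 7.3.
- Window anchored on the last dose actually given (cycles of 6, 4 and 2 weeks for lomustine, TMZ and ABT-414; 60% of controls on lomustine assumed): 6.7 / 11.3, window ratio 1.79.
- Window ending at progression, with no 35-day tail: 7.0 / 11.6. This is close to the cut-off in Protocol 8.2.3.7, which differs from the SAP's.

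**5. Would the remedy work?** In this model an exposure-adjusted rate has an expected ratio of 1.0 for an unrelated event. Within the first 8 weeks, mean time in the window is 1.78 months on control and 1.81 on ABT-414 (ratio 1.015). The crude 8-week percentages then differ by less than 0.4 points for monthly hazards from 0.03 to 0.20.

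**The case against.** **No planned inference is biased.** SAP 11.1 and Protocol 8.2.3.7 exclude formal safety comparisons. This stands: no test or confidence interval is affected. But the percentages will sit side by side, and reading across them is what such a table invites.

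**The context is already reported.** Exposure duration by arm, relationship to each drug as judged by the investigator, grade, and time to onset for keratopathy are all planned. This helps a careful reader. But a separate exposure table does not let anyone recover an adjusted incidence for a given event, and the onset analysis covers one event group only.

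**PFS is not treatment time.** A reader might infer that the plan expects ABT-414 patients to be treated 1.85 times as long as controls. The documents do not say so: they state no expected treatment duration. The PFS endpoint is centrally reviewed, whereas treatment decisions follow the local reading (Protocol 7.1.1.4). Treatment may continue after T2/FLAIR progression (7.1.1.1) and also stops for toxicity or refusal. The relevant ratio is that of the counting window, about 1.6, and it is itself an inference.

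**The size is conditional.** A reader might also infer that unrelated events will look 7 to 12 points more frequent. With the 35-day tail, that range needs control percentages of about 13% to 35%, a constant hazard, exponential stopping and a true PFS hazard ratio of 0.54. Exponential stopping puts about 39% of controls off treatment before the week 8 scan, and the model gives everyone a full 35-day tail although some PFS events are deaths. These limits stand; the figures are illustrations.

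**Protocol 1.7.** This section lists events at least 5% "more frequently than the lomustine/TMZ control group included headache, fatigue, constipation" and liver transaminase elevations. It is tempting to read this as a rule for naming drug effects, already distorted by exposure. It is a reporting threshold in background text on several studies, not a rule of this SAP. The same paragraph cautions that the constipation came mainly from the combination arm, at a rate similar to that with TMZ alone. Nothing there shows that exposure explains the differences observed.

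**Conclusion.** The gap is real: for general treatment-emergent, serious and grade 3 or higher events, the plan offers only crude percentages over a window whose length depends on treatment time.

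The size is conditional on three assumptions: treatment time follows the design PFS medians, stopping is exponential, and event hazards are constant and equal in all arms. Under these, the window is about 1.6 times longer on ABT-414, and an unrelated event seen in about 5%, 10%, 20% or 35% of controls appears roughly 3, 5.5, 9 or 12 points more often there. At a PFS hazard ratio of 0.70 the gap is about 3 to 5 points for control percentages of 10% to 20%. It is smaller again for front-loaded events, and there is none if PFS is equal.

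This is a weakness in descriptive reporting, not an error in a test. It deserves correction because it is largest in the scenario the trial is powered to detect.

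**What to change.** In SAP 11.2, keep the percentages. For the overview rows, serious events, events of grade 3 or higher, and preferred terms at 10% or more, add two descriptive columns per arm:

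1. **Exposure-adjusted incidence rate:** subjects with a first event per 100 patient-months, with time running from first dose to first event or to the end of the treatment-emergent window.
2. **Early incidence:** percentage of subjects with a first event in the first 8 weeks, when time under observation is nearly equal in all arms.

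Add no p-values, so the SAP 11.1 rule is unchanged.

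**Cost.** Two more columns per table, from dosing and event dates already collected. The rates assume a roughly constant hazard and can mislead for front-loaded events; the 8-week percentage offsets this.

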1.2 Chemotherapy and outcome in recurring glioblastoma

Once a glioblastoma recurs, the treatment options are usually limited and no uniformly accepted standard of care exists. The most important prognostic factors in this setting are age, performance status, use of steroids and size/number of enhancing lesions (Ref. 7, Ref. 8). Other factors of relevance may include re-resection (tumor burden), promoter methylation status of O6-methyl-guanine-methyl transferase (MGMT). Many patients deteriorate rapidly at the time of recurrence, making further treatment meaningless. Some patients have recurrences that allow re-resection but most patients have lesions inaccessible for surgery (e.g., involvement of the corpus callosum, deeply seated lesions, or lesions in eloquent areas). Re-irradiation is also being used, despite the risk of cumulative neuro-toxicity and this approach is feasible in patients with lesions of limited size (Ref. 9). The efficacy of re-irradiation in glioblastoma is however debated. Chemotherapy is commonly suggested for recurrent disease. Both nitrosoureas (in particular lomustine) and TMZ provide options for selected patients. Studies of retreatment with TMZ at the time of relapse suggest that this approach may be effective in selected patients: especially after a treatment free interval or in the presence of MGMT promoter methylation (Ref. 10). The RESCUE trial, on continuous daily dosing of TMZ in patients having relapsed after RT/TMZ analyzed outcome in relation to the interval between the end of initial chemotherapy and salvage TMZ treatment (Ref. 11). In the entire group, PFS-6 was 23.9% but PFS-6 in the patients relapsing more than two months after the end of TMZ was 35.7%, as opposed to only 7.4% in the patients relapsing after more than 6 cycles of adjuvant TMZ but while still on TMZ treatment. Of note, PFS-6 was 23.9% for patients relapsing during the first 6 cycles of adjuvant TMZ, but here no minimum interval between the end of RT and study entry was specified. The outcome in this last group is quite likely explained by the presence of pseudo-progression and radiation necrosis early after the end of RT, with likely spontaneous improvement over time even in the absence of treatment (Ref. 12, Ref. 13). With respect to OS, only 12 month OS was reported: this was 28% for patients relapsing more than 3 months after the end of TMZ adjuvant treatment and 14% for the patients relapsing within 3 months or during TMZ treatment. Historical data (EORTC 26981) suggest that 60% of randomized patients will relapse before 3 months after the end of adjuvant TMZ treatment, and 40% thereafter (relapses during RT or in the 3 months thereafter are not eligible). The data of EORTC study 26981 also suggest that two-thirds of patients that do not progress until more than three months after the end of TMZ will have a methylated MGMT promoter. There are quite some data available on the outcome of TMZ retreated relapsing glioblastoma patients. The important role of adequate patient selection for retreatment with TMZ is further supported by the initial results reported at ASCO 2014 of the German randomized phase II DIRECTOR trial on 'week on-week off' TMZ versus 'three weeks on-one week off'

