4.2 Design Diagram

This is a comparative randomized, open label, multicenter, multi-arm, Phase II study. The study will consist of three treatment arms; Arm 1 (ABT-414 plus TMZ), Arm 2 (ABT-414 monotherapy), and Arm 3 (mixed control arm of lomustine or TMZ). Subjects will be randomized in a 1:1:1 ratio at the EORTC headquarters after verification of the eligibility criteria discussed in Section 3 of the study protocol.

Arm 1: Subjects will be treated with ABT-414 1.0 mg/kg IV infusion over 30 to 40 minutes once every 2 weeks in combination with TMZ 150 mg/m² Day 1 to 5, for the first 28-day cycle, with dose escalation to 200 mg/m² in subsequent cycles in case of adequate tolerance and until one of the treatment withdrawal criteria has been met. In this Arm 1 the schedule of clinical and lab assessments follows the cycle of TMZ (a delay of TMZ delays the assessment schedule, withholding ABT-414 does not affect the assessment schedule).

Arm 2: Subjects will be treated with ABT-414 monotherapy 1.0 mg/kg IV infusion over 30 to 40 minutes once every 2 weeks until one of the treatment withdrawal criteria has been met.

Subjects in the control arm (Arm 3) will be treated according to the timing of relapse.

Arm 3A: Subjects relapsing during TMZ treatment or within the first 16 weeks after the first day of the last TMZ cycle will be treated with lomustine 110 mg/m² on Day 1 of every 42-day treatment period. Treatment will continue until one of the treatment withdrawal criteria has been met. Lomustine will be given for a maximum of 1 year.

Arm 3B: Subjects relapsing 16 weeks or more after the first day of the last TMZ cycle will be treated with TMZ 150 mg/m² on Day 1 to 5 for the first 28-day cycle, with dose escalation to 200 mg/m² in subsequent cycles in case of adequate tolerance. Treatment will continue until one of the treatment withdrawal criteria has been met.

Treatment should start within 96 hours from randomization. Treatment will be administered until one of the withdrawal criteria described in Section 5.4 of the study protocol has been met. Treatment at further progression will be according to investigators discretion.

Day 1 of the first cycle will be the first day when the study medication is taken.

A schematic of the study design is shown in [Figure 1](#). The study procedures for each visit are outlined in [Table 1](#).

Figure 1. Study Schematic

[figure not shown]

Table 1. Study Activities

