9.0 Study Drug Exposure and Compliance

9.1 Dosage

Analyses for the study drug (ABT-414/TMZ/lomustine) treatment will be performed on the Safety population. Longitudinal summary statistics for average dose administered during the study will be presented. The number and percentage of subjects at each treated dose will be presented longitudinally.

An overview of dose modification will be presented by treatment arm, consisting of the number and percentage of subjects who had at least one dose modification for each of ABT-414/TMZ/lomustine throughout the study.

Dose modification of ABT-414/TMZ/lomustine will be summarized for each course/cycle. The frequency and percentage of subjects will be summarized by treatment arm, and reasons for dose modification will also be summarized.

For dose intensity and relative dose intensity of ABT-414 (Arms 1 and 2 only), the following calculation rules are applied:

- The dose intensity of ABT-414 is calculated on actual treatment duration (in weeks) and actual treatment dose received (total dose received in mg/kg). Whenever the treatment is given in cycles and the last planned day of treatment is not the last day of the cycle, the total duration of the treatment must account for this by adding the appropriate number of days to complete the last cycle. That is, if ABT-414 stopped on Day X of a 28-day cycle, the total treatment duration in days is [date of last injection] – [date of first injection] + 1 + (28-X).

- The dose intensity (mg/kg/week) of ABT-414 is the ratio of the total dose received (mg/kg, adjusted by weight) to the total treatment duration (weeks).

$$DI_{observed} (mg / kg / week) = \frac{Total\ dose\ (mg / kg)}{Actual\ total\ treatment\ duration\ (weeks)}$$

- The relative dose intensity is calculated as the ratio of the dose intensity as calculated above to the dose intensity indicated in the protocol, expressed in percent (%). To obtain a correct ratio, the theoretical dose intensity will be expressed in the same units of dose and treatment duration as those used for the actual dose intensity.

$$DI_{protocol} (mg / kg / week) = \frac{Dose\ per\ cycle\ (mg / kg)}{Theoretical\ duration\ of\ one\ cycle\ (weeks)}$$

- The relative dose intensity is usually presented using median and ranges, and by a distribution into categories (relative dose intensity $\leq 70\%$, $> 70 - 90\%$, $> 90 - 110\%$, $> 110 - 120\%$, $> 120\%$).

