9.3 Compliance

Analyses for compliance will be performed on subjects who received at least one dose of TMZ.

The frequency and percentage of subjects will be summarized by treatment arm for (1) at least 80% compliant of TMZ at every cycle in the investigator's opinion, (2) at least 80% compliant of TMZ at all but one cycle in the investigator's opinion, (3) less than 80% compliant of TMZ at more than one cycle in the investigator's opinion.

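### SAP 11.2 and 9.1 give TMZ- and lomustine-specific percentages for a mixed Arm 3 with no stated denominator and no 3A/3B split, so read naturally they are not rates among subjects given the drug

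*SAP*

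**What the plan says.** SAP 4.2 defines three arms and describes the control as "Arm 3 (mixed control arm of lomustine or TMZ". Within it, early relapses (3A) get lomustine and late relapses (3B) get TMZ. SAP 5.0 places a subject in Arm 3 of the Safety population on one dose of either drug, and moves Arm 1 subjects who took TMZ but no ABT-414 into Arm 3.

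SAP 11.2 then states: "An overview of AEs will be presented, by treatment arm and overall", as numbers and percentages of subjects. Among the listed categories is "Any treatment-emergent adverse event that is rated as a reasonable possibility of being related to TMZ". Five more row types are drug-specific: grade 3/4 related, serious related, and leading to discontinuation, dose reduction or interruption. Each appears for TMZ and again for lomustine. No denominator is given for any of them.

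SAP 9.1 gives, by treatment arm, "the number and percentage of subjects who had at least one dose modification for each of ABT-414/TMZ/lomustine". Elsewhere the SAP does name an exposed subset. SAP 9.3 says: "Analyses for compliance will be performed on subjects who received at least one dose of TMZ". SAP 11.4 names Arms 3A and 3B separately when it lists collection times.

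**The concern.** By design, a subject in 3A cannot have a TMZ-related event on study, and a subject in 3B cannot have a lomustine-related one. If the percentage base is all of Arm 3, the TMZ row cannot exceed the TMZ share of the arm, and the lomustine row cannot exceed the lomustine share. In Arm 1 every as-treated subject is meant to have had TMZ, so the same row there is close to a per-exposed rate. A reader comparing across the TMZ row would be comparing two different quantities.

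This matters because Protocol 1.8 says that having TMZ-treated patients in the control arm should help to separate out what TMZ contributes. A table that blends them with lomustine-treated patients makes that harder on the safety side.

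**Working it through.** The documents give no figure for these denominators or for the size of the dilution, so only the arm size can be reproduced.

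**Inputs**
- Arm size: Protocol 8.1.1 assumes 10 patients a month for 12 months and then 20 a month to month 18. 12 × 10 + 6 × 20 = 240, which matches the stated total. At 1:1:1, 240 / 3 = 80 per arm.
- Split of Arm 3: Protocol 1.2 cites historical data suggesting that "60% of randomized patients will relapse before 3 months after the end of adjuvant TMZ treatment, and 40% thereafter". Protocol 1.8 equates that 3-month cut with 16 weeks from the first day of the last TMZ cycle. So about 0.60 × 80 = 48 subjects on lomustine and 0.40 × 80 = 32 on TMZ.
- Assumption: the TMZ-related rate per TMZ-treated subject, p, is the same in Arm 1 and Arm 3B.

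**Formulas.** Let s be the TMZ share of Arm 3 and q the lomustine-related rate per lomustine-treated subject.
- TMZ row: Arm 1 shows p and whole Arm 3 shows s × p, so the ratio is 1/s.
- Lomustine row: whole Arm 3 shows (1 − s) × q, a dilution of 1/(1 − s). Arms 1 and 2 are zero by design.

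| TMZ share s | On TMZ / on lomustine, of 80 | TMZ rows, Arm 1 ÷ Arm 3 | Lomustine rows, dilution in Arm 3 |
|---|---|---|---|
| 30% | 24 / 56 | 3.3 | 1.43 |
| 40% | 32 / 48 | 2.5 | 1.67 |
| 50% | 40 / 40 | 2.0 | 2.0 |

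If the true TMZ share is 40%, the 95% binomial range for 80 patients is 24 to 41 on TMZ, which gives a ratio from 80/24 = 3.3 to 80/41 = 2.0.

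**Illustration with p = q = 30% (assumed), s = 40%**
- TMZ row: Arm 1 30%; Arm 3 on all 80, 0.40 × 30% = 12%; Arm 3B on 32, 30%. Overall column: 30% × (80 + 32)/240 = 14%.
- Lomustine row: Arm 3 on all 80, 0.60 × 30% = 18%; Arm 3A on 48, 30%. Overall column: 30% × 48/240 = 6%.

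**Effect of as-treated reclassification.** If k Arm 1 subjects who took only TMZ move to Arm 3, the ratio becomes (80 + k)/(32 + k). For k = 2 it is 82/34 = 2.4, and for k = 8 it is 88/40 = 2.2. The rule softens the effect slightly and does not remove it.

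With subjects who received the drug as the base, equal toxicity per TMZ-treated subject gives a ratio of 1.0.

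**The case against.** The strongest reply is that nothing tabulated is false. The share of Arm 3 with a TMZ-related event is a true description of that arm, and SAP 11.2 never says that it is a per-exposed rate. Counts accompany percentages and SAP 9.2 summarises exposure by drug within arm, so a careful reader could rebuild the per-exposed rates for Arm 3. SAP 11.1 excludes statistical comparisons, p-values and confidence intervals for safety, so no test is affected. All of this stands, and it limits the point to presentation.

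Several stronger readings are tempting, and the documents do not support them.
- **That the SAP specifies whole Arm 3 as the base.** It is the natural reading of a by-arm table on this Safety population, but it is inferred.
- **That the 2.5-fold contrast covers lomustine rows.** Arm 1 receives no lomustine, so no such contrast exists.
- **That 60% of Arm 3 never took TMZ.** Eligibility requires prior RT/TMZ. The figure concerns study treatment only and is a historical expectation.
- **That all-cause rows credit TMZ toxicity to ABT-414.** Those rows are not diluted. They do reflect drug mix: an event at 20% on TMZ and 5% on lomustine (assumed) gives 0.4 × 20% + 0.6 × 5% = 11% in Arm 3 against 20% in Arm 1 with no ABT-414 effect. But ABT-414 monotherapy (Arm 2) sits in the same table and would show no such excess.
- **That the constipation finding in Protocol 1.7 proves harm.** The paragraph that reports an excess over the combined control also says it was "mainly accounted for by the ABT-414/TMZ combination arm, for which the rate was similar to that of subjects receiving TMZ monotherapy". This shows the sponsor making the split when interpreting data. It does not show a wrong conclusion, and its 5% screen belongs to a summary of ABT-414 groups across four studies.
- **That SAP 9.3 sets a rule which 11.2 breaks.** TMZ compliance has no meaning in someone not given TMZ, so that restriction was unavoidable. It shows only that the SAP can name an exposed subset where it wants one.

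**Conclusion.** The point holds as a reporting weakness that is cheap to correct. The drug-specific rows in SAP 11.2 and the dose-modification overview in SAP 9.1 have no stated denominator. On the natural reading, their Arm 3 percentages are diluted by subjects not given the drug on study.

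For TMZ rows, the apparent Arm 1 to Arm 3 ratio under equal toxicity is about 2.5 at the planning split, and 2.0 to 3.3 across TMZ shares of 50% to 30%. For lomustine rows, the dilution within Arm 3 is about 1.67-fold. These sizes rest on three things: the inferred denominator, a historical 60:40 split that the trial's own Arm 3 may not match, and equal per-exposed TMZ toxicity in Arms 1 and 3B. Every share in that range leaves a substantial distortion, so the case for the change does not depend on the exact split.

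**What to change.** In SAP 9.1 and 11.2:
- State that each drug-specific row is a percentage of Safety-population subjects who took at least one dose of that drug on study.
- Show Arm 3A (lomustine) and Arm 3B (TMZ) as columns beside total Arm 3.
- For the adverse-event overview, also show Arm 1 against Arm 3B within the late-relapse stratum (16 weeks or more). Arm 1 contains both relapse strata and Arm 3B only the late one, so the unrestricted contrast would mix populations. Label it an as-treated descriptive comparison. The reclassification rule in SAP 5.0 means that it is not strictly randomised.

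SAP 12.0 leaves the related-event rows in the EORTC analysis too, so the wording should cover both sets of tables.

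The cost is SAP text and extra table columns. No new data are needed, since relapse timing is already a stratification factor. The downside is smaller denominators, about 32 for 3B and 48 for 3A, which is acceptable in descriptive tables.
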